5.1 MAIN OUTCOMES

The main outcome of the study is the prevalence of off-label prescribing among new users of olodaterol. As a secondary outcome, the prevalence of off-label prescribing among new users of indacaterol will be assessed.

According to age and the presence of a recorded diagnosis of COPD and/or asthma, new users of olodaterol and new users of indacaterol will be classified into the following categories ([Table 4](#)):

- On-label prescribing: adults (aged ≥ 18 years at the index date) with a recorded diagnosis of COPD, with or without asthma
- Off-label prescribing:
 - Adults (aged ≥ 18 years at the index date) with a recorded diagnosis of asthma and without a recorded diagnosis of COPD, and
 - All children (aged < 18 years), irrespective of whether they have a recorded diagnosis of COPD (unlikely), asthma, or other respiratory disease
- Potential off-label prescribing: adults (aged ≥ 18 years) without a recorded diagnosis of COPD or asthma:
 - To further characterise these patients, recorded diagnosis of “other respiratory comorbidities” among these patients will be described (see conditions included in [Section 5.3.4](#)). The possibility of these patients having “probable COPD” will also be

Proprietary confidential information © 2017 Boehringer Ingelheim International GmbH or one or more of its affiliated companies

explored. Probable COPD will be defined by the presence of at least two prescriptions of long-acting beta2-agonist (LABA), long-acting muscarinic antagonist (LAMA), or inhaled glucocorticosteroid (ICS) (or combination) after the age of 40 years but not before (see lists of medications in [Annex Table 1-6](#)).

Table 4 Classification of patients according to age and indication of olodaterol and indacaterol

Recorded diagnosis ¹	Age	On-label prescribing: indication of COPD	Off-label prescribing	Potential off-label prescribing
COPD	≥18	Yes		
COPD and asthma	≥18	Yes		
Children, irrespective of any recorded diagnosis	<18		Yes	
Asthma (no COPD)	≥18		Yes	
No COPD, no asthma ²	≥18			Yes

COPD = Chronic Obstructive Pulmonary Disease.

- 1 Diagnosis recorded at any time before or on the index date and up to 30 days after the index date.
- 2 To further characterise adult patients with no COPD and no asthma, “potential COPD” and “other respiratory conditions” will be described among these patients.

A diagnosis of COPD or asthma will be defined as having one or more COPD or asthma diagnoses recorded in the database before the index date and up to 30 days following the index date. The *International Statistical Classification of Diseases and Related Health Problems, 10th Revision* (ICD-10) and *International Classification of Primary Care* (ICPC) codes to identify patients with COPD and asthma are detailed in [Table 5](#).

Table 5 ICD-10 and ICPC diagnosis codes to identify patients with COPD and asthma

ICD-10 code description	ICD-10 code ¹	ICPC code ¹
COPD	J41-J44	R95
Chronic bronchitis ²	J41-J42	R78, R91
Emphysema	J43	—
Other COPD	J44	—
Asthma	J45, J46	R96

ICD-10 = *International Statistical Classification of Diseases and Related Health Problems, 10th Revision*;
ICPC = *International Classification of Primary Care*.

1. Data sources use different coding systems with different degrees of granularity; thus, subclassifications will be adapted to each database.
2. The use of ICD-10 code J40 “Bronchitis, not specified as acute or chronic” to define COPD will be assessed in the data source-specific definitions.

Proprietary confidential information © 2017 Boehringer Ingelheim International GmbH or one or more of its affiliated companies

The indication for the prescribing of medications is not recorded in either the PHARMO databases or the Danish National Registries; indication is available but may be incomplete in the IMS RWE LPD. Therefore, when indication is not available, the indication of treatment and potential off-label use of olodaterol and indacaterol will be inferred from COPD and asthma diagnosis recorded at any time before or on the index date or up to 30 days after the index date and from the clinical review of information in computerised patient profiles. In addition, the time since first COPD diagnosis, i.e., time between the first recorded diagnosis of COPD in the database and the index date, will be ascertained for new users of olodaterol and indacaterol. Additional database-specific specifications on COPD, asthma, and on-label/off-label use are presented in Section [9.2](#).

A random sample, stratified by age (18-39 years, ≥ 40 years) and sex, of up to 100 patient profiles from new users of each medication before and up to 30 days after the first exposure to the respective drug will be reviewed to confirm that the algorithms and codes developed to identify COPD and asthma are correct, i.e., that no codes have been missed and that the time window proposed is appropriate for the specific data source. The 100 olodaterol and 100 indacaterol new users will be randomly selected among the following groups by sex and age: 25 females aged 18-39 years, 25 males aged 18-39, 25 females aged ≥ 40 years, and 25 males aged ≥ 40 years; if there are less than 25 patients in the younger age groups, the remaining patient profile reviews, up to 25, will be done in the older age groups). Patient profiles are chronological listings of the routinely recorded codes that represent clinical events recorded in the study databases for individual patients. These listings include general practitioner diagnoses (if available, depending on the data source), outpatient and hospital discharge diagnoses and procedures, and dispensings of medications. The clinical review of patient profiles will provide more accurate information for evaluation of the indication and potential off-label use of olodaterol and indacaterol than use of codes alone. This information will be useful for developing clinical algorithms that can be applied to the evaluation of all new users of olodaterol and indacaterol. Patient profile review will be performed after the initial application of the electronic algorithm; if needed, the algorithms will be modified. The algorithm developed after patient profile review will be used for all the analyses to be performed for the interim and final study reports.

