in each country). A course of systemic glucocorticosteroids will be defined as treatment involving consecutive dispensings of systemic glucocorticosteroids with less than 7 days between the end of days of supply of one dispensing and the date of the next dispensing. The variable “second course of systemic glucocorticosteroids” will be categorised as “no” if the patient had 0 or 1 course of systemic glucocorticosteroids during the 12 months before or on the index date or “yes” if the patient had at least two courses of systemic glucocorticosteroids during the 12 months before or on the index date.

- Diagnosis of COPD exacerbation without hospitalisation: an outpatient (GP, outpatient hospital clinic, or pulmonologist) ICD-10 code or ICPC code for COPD exacerbation (ICD-10 code: J44.1; free-text search in the PHARMO-GP), acute bronchitis (ICD-10 codes: J20, J21, J22, J40; ICPC code: R78), or pneumonia (ICD-10 codes: J09-J18; ICPC code: R81) within 12 months before or on the index date.
- Oxygen therapy: a prescription or dispensing for oxygen therapy (ATC code: V03AN01) within 12 months before or on the index date.
- Nebuliser therapy (to be identified in each data source using national drug codes).
- Emphysema: an outpatient or inpatient (primary or secondary hospital discharge or outpatient hospital clinics) code for emphysema at any time before or on the index date (ICD-10: J43; free-text search in the PHARMO-GP).

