5.3.4 Respiratory comorbidity and allergies

Respiratory comorbidities other than COPD or asthma will be conditions recorded at any time before or up to 30 days after index date and will be ascertained using the diseases and codes listed in [Table 9](#). These will be described for the purpose of characterising the study population overall and the subgroup of patients classified as potential off-label users, but do not constitute “suspected off-label indications.”

Table 9 Respiratory comorbidity and allergies

Disease description ¹	ICD-10 code	ICPC code
Pneumonia	J09-J18	R81
Allergic rhinitis	J30	R97
Bronchiectasis	J47	—
Lung diseases due to external agents	J60-J69	—
Acute bronchitis or bronchiolitis ²	J20, J21, J22, J40	R78
Other respiratory conditions	J80-J99	R99

COPD = Chronic Obstructive Pulmonary Disease; ICD-10 = *International Statistical Classification of Diseases and Related Health Problems, 10th Revision*; ICPC = *International Classification of Primary Care*.

¹ Other respiratory comorbidities of interest may be described depending on data availability.

² The use of ICD-10 code J40 “Bronchitis, not specified as acute or chronic” will be assessed in the data source-specific definitions.

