7.5.2 Patient profile review to evaluate COPD and asthma algorithms

A description of the patient profile review process is presented in Section [5.1](#). Patient profiles will be created on a random sample, stratified by age (18-39 years, ≥ 40 years) and sex, of 100 new users of each study drug olodaterol and indacaterol. Results of the manual review of the patient profiles will be described and compared with the treatment indications identified through the electronic algorithms based on medical codes. These results will be described in the study report. Results reporting COPD, asthma, and “no COPD no asthma” as identified by the electronic algorithm and after patient profile review will be presented (Shell Table 11).

Proprietary confidential information © 2017 Boehringer Ingelheim International GmbH or one or more of its affiliated companies

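### SAP Table 5 uses ICPC code R78 to identify COPD, while SAP 5.3.3 and Table 9 treat R78 as acute bronchitis; on the visible text one R78 record makes a PHARMO-GP adult on-label

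*SAP*

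**What the plan says.** The main outcome depends on who has a recorded COPD diagnosis. SAP 5.1 states: "A diagnosis of COPD or asthma will be defined as having one or more COPD or asthma diagnoses recorded in the database". The window is all available history (from 2006 for the PHARMO subset with GP data, SAP section 5) plus 30 days after index. Table 5 lists the codes. Its ICPC column gives R95 for COPD, R78 and R91 for chronic bronchitis, and R96 for asthma.

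The SAP uses R78 in two other places. In 5.3.3, an outpatient exacerbation can be identified by "acute bronchitis (ICD-10 codes: J20, J21, J22, J40; ICPC code: R78"). In Table 9, R78 stands in the row "Acute bronchitis or bronchiolitis", again beside J20, J21, J22 and J40. The text introducing that table reads: "Respiratory comorbidities other than COPD or asthma will be conditions recorded at any time before or up to 30 days after index date".

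SAP 7.5.1 classifies in order: children are off-label; adults with COPD are on-label whatever else they have; adults with asthma and no COPD are off-label; the remaining adults are potential off-label.

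Two passages leave room for later change. On database-specific rules, 5.1 says: "Additional database-specific specifications on COPD, asthma, and on-label/off-label use are presented in Section" 9.2. On the profile review it says: "Patient profile review will be performed after the initial application of the electronic algorithm; if needed, the algorithms will be modified".

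**The concern.** The same code cannot both identify COPD and mark a condition other than COPD. The two uses are also out of line across coding systems: on the ICD-10 side J20-J22 are not COPD codes, yet the ICPC code that the SAP pairs with them is.

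The primary outcome in PHARMO-GP is at stake. The objective in protocol section 8 is the share of new users without COPD, and protocol 9.3.2 regards GP information as the most appropriate for assessing it. On the visible text, one acute bronchitis recorded years earlier would be enough to count a patient as on-label.

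There are smaller knock-on effects:
- R78-only patients aged 40 or older enter the COPD severity table, where R78 also counts towards exacerbations. One such record does not make a patient severe, because two exacerbations are needed.
- Time since first COPD diagnosis can start at an acute bronchitis.
- No PHARMO-GP adult classed as potential off-label can have an R78 record, although Table 9 is meant to describe that group.

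**Working it through.** The SAP gives no figure to reproduce. The check applies its rules, then shows what the size would depend on.

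**Step 1: classification** (Table 5 ICPC codes and the 7.5.1 order).

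| Codes in a PHARMO-GP adult | R78 counted as COPD | R78 not counted |
|---|---|---|
| R78 only | on-label | potential off-label |
| R78 and R96 | on-label | off-label (asthma) |
| R96 only | off-label (asthma) | off-label (asthma) |
| R95 or R91 | on-label | on-label |
| none of these | potential off-label | potential off-label |

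Children are off-label either way. SAP Table 3 shows ICPC in PHARMO-GP only, so Denmark and France are unaffected. Every change is towards on-label.

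**Step 2: shift in the reported share.** Let p be the share of PHARMO-GP adult new users with no COPD code other than R78, and q the fraction of these with R78. Without R78 the combined off-label and potential off-label share is p; with it, p(1-q). Both p and q are assumptions.

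- At p = 20%, q = 10, 30 and 50% give 18.0, 14.0 and 10.0%.
- If that 20% were 5% asthma off-label and 15% potential off-label with equal q, q = 30% gives 3.5% and 10.5%.
- At an assumed 800 adults and q = 30%, the exact (Clopper-Pearson) 95% intervals are 17.3-22.9% without R78 and 11.7-16.6% with it. The choice of code could outweigh sampling error.

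**Step 3: bias against true COPD status.** Let c be the share of R78-only patients (R78 and no other COPD code, with or without asthma) who truly have COPD, and d the share with COPD among patients with neither R78 nor another COPD code. The true share without COPD is p[(1-q)(1-d) + q(1-c)].

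If d = 0, counting R78 understates it by the relative amount q(1-c)/(1-qc):

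| q | c = 0% | c = 25% | c = 50% | c = 75% |
|---|---|---|---|---|
| 10% | 10.0% | 7.7% | 5.3% | 2.7% |
| 30% | 30.0% | 24.3% | 17.6% | 9.7% |
| 50% | 50.0% | 42.9% | 33.3% | 20.0% |

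If d > 0 the picture changes. The error is p[(1-q)d - q(1-c)] with R78 and p[(1-q)d + qc] without it. They are equal in size at c = 0.5 - (1-q)d/q. With q = 10% and d = 5% this is 0.5 - 0.9 × 0.05/0.1 = 0.05, so removing R78 is the more accurate choice only if fewer than 5% of R78-only patients have COPD. With p = 20%, q = 10%, d = 20% and c = 0, the truth is 0.20 × (0.9 × 0.8 + 0.1) = 16.4%. The report is 18.0% with R78 and 20.0% without it, so both are too high and the version with R78 is closer.

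**Step 4: PHARMO as a whole.** SAP Table 2, footnote 1, puts about 1 million of 4 million patients in PHARMO-GP. Assume the same one in four among new users, and write p' for the share outside. The relative shift is 0.25pq/(0.25p + 0.75p'). With p' = p it is q/4. With p = 20% and p' = 60% it is 0.05q/0.50 = q/10.

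**The case against.** The strongest reply is that Table 5 is not the last word. ICPC is used only in PHARMO-GP, and the database-specific COPD rules are in Section 9.2, which is not in the supplied text. Footnote 1 of Table 5 allows subclassifications to be adapted. The profile review may change the algorithm before the interim and final analyses, and SAP 7.5.2 adds: "Results of the manual review of the patient profiles will be described and compared with the treatment indications identified through the electronic algorithms". That comparison could expose false positives. This stands as a limit: a reader might infer that R78 will certainly be counted as COPD in the final analysis, and the documents do not show that. But nothing visible removes R78, the general text would still contradict itself, and the check spelled out in 5.1 is for missed codes and the time window, not for a code that is too broad.

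A second reply is that R78 is the ICPC counterpart of J40, bronchitis not specified as acute or chronic, whose use "will be assessed in the data source-specific definitions". The footnote marker in Table 5 does sit on the chronic bronchitis row. This reading is possible, but the footnote names only J40, and the SAP pairs R78 with J20-J22 as well.

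A third reply is that keeping R78 may be the more accurate choice. SAP 7.3 worries about missed COPD when hospital diagnoses are used alone, and 5.1 plans to look for probable COPD among adults with no recorded COPD or asthma. Step 3 shows that this reply stands: with undiagnosed COPD in that group, the definition with R78 can be closer to the truth.

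**Conclusion.** The contradiction between Table 5 and both 5.3.3 and Table 9 is explicit. On the visible text it moves R78-only PHARMO-GP adults out of potential off-label, and adults with R78 plus asthma out of off-label. Compared with a definition without R78, both shares can only be reported lower.

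The relative fall in the combined PHARMO-GP adult share is q. For all of PHARMO it is at most about q/4, provided that one in four new users is GP-linked and that the share outside PHARMO-GP is equal or higher. SAP 7.3 suggests it is higher, since hospital diagnoses alone overestimate potential off-label use.

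A reader might infer that the plan understates true off-label use by a known amount, or that dropping R78 must improve accuracy. Neither follows. The net bias depends on q, on how many R78-only patients have COPD, and on undiagnosed COPD among patients with neither code; the documents give none of these. The point should be fixed because the primary outcome should not rest on a code with two meanings. Confidence is moderate because Section 9.2 cannot be seen.

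**What to change.** Reconcile Table 5 with 5.3.3, Table 9 and Section 9.2. By default, remove R78 from the COPD list, keep R95 and R91, and leave R78 in Table 9 and as an exacerbation marker. If R78 is kept as the counterpart of J40, say so and give the reason.

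Whichever definition serves the main analysis, report the PHARMO-GP main outcome with and without R78-only patients counted as COPD, separately for asthma off-label and potential off-label.

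The cost is one code in a SAP table, a rerun of the PHARMO-GP classification and one extra tabulation; no new data are needed. The downside of removal is some loss of COPD sensitivity. For adults without asthma this is partly covered, because they fall into potential off-label, where probable COPD is already to be described. Adults with R78 plus asthma get no such description, so the two-way report matters most for them.

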#### 9.3.2.1 On-label prescribing: indication of COPD

The indication of COPD is defined as any patient with a diagnosis of COPD, chronic bronchitis, or emphysema recorded in the database at any time before the index date or at the index date. Because COPD can occur in association with asthma, patients with a recorded diagnosis for both COPD and asthma will be considered on-label. [\[R14-0350\]](#) [\[R07-2620\]](#) [\[R08-1492\]](#).

For this study, classification of COPD status will be based on general practice diagnoses and hospital outpatient and inpatient discharge diagnoses. No validation data are available for COPD diagnoses recorded in PHARMO. In general, in Denmark and Sweden, validation has been performed for COPD diagnoses ascertained via hospital (inpatient and outpatient) diagnoses. ICD diagnoses codes for COPD have shown a good positive predictive value (PPV). In the Danish National Registers, the PPV for the hospital discharge diagnosis of COPD (ICD-10 code J44) was 92%. [\[R14-0359\]](#) In Sweden, a COPD validation study showed that the COPD diagnosis (ICD-9: 491-492, 496; ICD-10: J41-J44) recorded in the National Inpatient Registry was considered as proven in 21.7% of cases, probable in 35.5%, possible in 34.0%, uncertain in 2.1%, and unlikely in 7.0%. [\[R14-0456\]](#) The proportion of patients with asthma misclassified as having COPD was 2.1%, and the overall degree of misclassification was less than 10%. The registry was considered of acceptable validity for epidemiological research of COPD.

The ICD-10 and ICD-9 codes to identify the diagnosis of COPD are detailed in [Table 3](#). Diagnosis codes include COPD, chronic bronchitis, and emphysema.

Table 3 ICD-10 and ICD-9 diagnoses and codes to identify patients with COPD

| ICD-10 Code Description                     | ICD-10 Code | ICD-9 Code |
|---|-------------|------------|
| Chronic bronchitis                          | J41-J42     | 491        |
| Emphysema                                   | J43         | 492        |
| Other COPD                                  | J44         | 496        |
| COPD with acute lower respiratory infection | J44.0       | —          |
| COPD with acute exacerbation, unspecified   | J44.1       | —          |
| Other specified COPD                        | J44.8       | —          |
| COPD, unspecified                           | J44.9       | —          |

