### 9.3.2.2 Off-label prescribing

Patients without a recorded diagnosis of COPD at any time before the index date or patients with a recorded diagnosis of asthma in the absence of a diagnosis for COPD will be considered off-label users. The off-label prescribing of olodaterol and indacaterol for the treatment of asthma is of special interest because this class of medication is often used in asthma but olodaterol and indacaterol have not been developed or approved for asthma.

Few studies have examined the validity of ICD codes for identifying patients with asthma. In a validation study conducted in Sweden, the PPV for the diagnosis of asthma (ICD-10 J45) associated with visits to outpatient specialty clinics and inpatient stays and recorded in the National Patient Registry among patients 18 to 45 years of age treated with asthma medications was 89% (95% confidence interval, 83%-93%). [R14-0349] The proportion of subjects misclassified as COPD was 1.6%. In another study conducted in the RAMQ Medical Services database of the province of Quebec in Canada, the PPV for having one or more recorded diagnoses of asthma (ICD-9 493) over a 1-year period in patients aged 16 to 44 years was 75% when the diagnosis was recorded by respiratory physicians and 67% when it was recorded by family physicians. The PPV increased to 77% for respiratory physicians and to 78% for family physicians when two or more recorded diagnoses of asthma were required. [R14-0352] Another study conducted in children under 4 years of age using data from the Rochester Epidemiology Project database showed that the overall agreement of ICD code 493 and information from the medical chart was 81.6%. [R14-0351]

The ICD-10 and ICD-9 codes to identify patients with asthma are detailed in Table 4.

Table 4 ICD-10 and ICD-9 diagnoses and codes to identify patients with asthma

| ICD-10 Code Description       | ICD-10 Code | ICD-9 Code         |
|-------------------------------|-------------|--------------------|
| Asthma                        | J45         | 493                |
| Predominantly allergic asthma | J45.0       | 493.0  |
| Non-allergic asthma           | J45.1       | 493.1  |
| Mixed asthma                  | J45.8       | —                  |
| Asthma, unspecified           | J45.9       | 493.9  |
| Chronic obstructive asthma    | —           | 493.2  |
| Other forms of asthma         | —           | 493.8              |

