5. OUTCOMES

For each patient, the observation period will start at the index date and look retrospectively for all available historical data and prospectively for up to 30 days after the index date to identify potential off-label use (Figure 1). The index date is defined as the date of the first recorded dispensing/prescription of olodaterol or indacaterol during the study period in each data source (see Table 1). In each country, new users of olodaterol and indacaterol will be identified in the databases, which record information on the medications prescribed by the physicians or dispensed by pharmacies. Evaluation of off-label use and diagnosis of COPD, asthma, or other respiratory conditions will be assessed using all available information in the database before the index date (as far back in time as records in the data source are available)—i.e., 01 Jan 1994 in Denmark, 1998 in PHARMO (1998 for total patient set and 2006 for subset with GP data available), and 1994 in IMS RWE LPD (1994 for GP panel and 2007 for pulmonologist panel) and up to 30 days after index date. Characterisation of new users based on demographic and other non-respiratory comorbidities will be assessed using all available information in the database before the index date, unless otherwise specified. Medication use, severity of COPD, and health care resource utilisation will be assessed for the 1-year period before the index date. Database-specific specifications to define the variables of interest in each data source are included in Section 9.2.

Figure 1 Time periods for defining key study variables

^a“Other respiratory conditions” are respiratory comorbidities other than COPD or asthma recorded at any time before or up to 30 days after index date and will be ascertained using the diseases and codes listed in Table 8. These will be described for the purpose of characterising the study population overall and the patients classified as potential off-label users.

Proprietary confidential information © 2017 Boehringer Ingelheim International GmbH or one or more of its affiliated companies

The type of data available varies in each database and is summarised in [Table 2](#).

Table 2 Selected characteristics of the study databases

Type of data	PHARMO, the Netherlands	National Registers, Denmark	IMS RWE LPD, France
Hospital inpatient discharge diagnoses	Yes	Yes	No
Hospital inpatient procedures	Yes	Yes	No
Hospital/clinic outpatient diagnoses	No	Yes	No

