7.5 MAIN ANALYSES

7.5.1 Clinical indication and evaluation of off-label and potential off-label use

A detailed description of the definition of COPD indication and on-label and off-label use is presented in Section [5.1](#). The prevalence of on-label and off-label new users and 95% confidence interval will be presented for olodaterol and indacaterol. Confidence intervals will be calculated using the Clopper-Pearson method for the binomial distribution [[R06-1080](#)]. Patients will be classified hierarchically:

- 1. All children will be classified as off-label, irrespective of their diagnosis.
- 2. All adult patients with a diagnosis of COPD will be considered on-label irrespective of whether they have a diagnosis of asthma or any other respiratory condition.
- 3. All adults without a COPD diagnosis and with a diagnosis of asthma will be classified under the group of “asthma only,” irrespective of whether they have any other respiratory condition. These patients will be classified as off-label.
- 4. All adults with no COPD and no asthma diagnosis will be classified as potential off-label. Among these patients, “probable COPD” and “other respiratory conditions” will be described. These will not be mutually exclusive, patients can have one or more of the respiratory conditions listed and “probable COPD.” Patients with no “other respiratory conditions” and no “probable COPD” will be classified under “No history of recorded respiratory conditions and no probable COPD.”

Results for the main analysis will be presented overall (Shell Table 10.1) and separated by age group (< 18, 18-29, 30-39, 40-49, 50-59, 60-69, 70-79, 80+ years; Shell Tables 10.2 through 10.9).

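### One COPD code from any year makes an adult on-label whatever the asthma record, and no visible analysis shows how false COPD codes would change the main prevalence

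*SAP*

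**What the plan says.** SAP 5.1 defines the classifying diagnoses: COPD or asthma "will be defined as having one or more COPD or asthma diagnoses recorded in the database before the index date", with the window extended to 30 days after it. SAP section 5 sets the lookback at "as far back in time as records in the data source are available", which is 1994 in Denmark, 1998 in PHARMO (2006 for GP data), and 1994 in the French GP panel (2007 for pulmonologists). The documents supplied require no repeat or recent record.

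SAP 7.5.1 then ranks the codes: "All adult patients with a diagnosis of COPD will be considered on-label irrespective of whether they have a diagnosis of asthma". For those with neither code, "All adults with no COPD and no asthma diagnosis will be classified as potential off-label", and within the main analysis only this group is examined further, for probable COPD and other respiratory conditions. The main prevalences carry Clopper-Pearson 95% intervals.

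Protocol 9.3.2.1 gives error rates for COPD codes. In the Danish registers "the PPV for the hospital discharge diagnosis of COPD (ICD-10 code J44) was 92"%. For the Swedish inpatient registry, "The proportion of patients with asthma misclassified as having COPD was 2.1%, and the overall degree of misclassification was less than 10"%. It states that PHARMO has no validation data for COPD diagnoses.

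**The concern.** The regulators asked for this study because of possible use in asthma (protocol section 7). An asthma patient with one stray COPD code, perhaps decades old, leaves the off-label count. The plan accepts a single code here, although its own definition of probable COPD needs at least two prescriptions.

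SAP 7.3 discusses only the opposite error, in which hospital codes miss COPD and inflate off-label use. The Clopper-Pearson interval reflects sampling error alone. A reader of the main table would therefore see a narrow interval with no indication of how far the result depends on lone COPD codes.

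There is also an identifiable source of such codes. SAP Table 5 lists ICPC R78 under chronic bronchitis, so it counts as COPD. SAP Table 9 and the exacerbation definition in SAP 5.3.3 use R78 for acute bronchitis. As written, one GP record of acute bronchitis could make an adult with asthma on-label in PHARMO-GP.

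**Working it through.** **1. Reproduce the plan's precision figures.** Exact Clopper-Pearson limits match all 20 cells of protocol Table 9 to the printed decimal. For 10% they are 6.8-14.0 (n = 300), 8.0-12.3 (n = 800), 8.7-11.4 (n = 2,000) and 9.2-10.9 (n = 5,000). SAP 7.5.1 names the same method for the main outcome.

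**2. Inputs.**
- q = share of new users with no COPD code. The documents give no value, so 10% is assumed, with 5% and 20% as a range.
- f = share of COPD-coded users who do not have COPD. From protocol 9.3.2.1: f = 1 - 0.92 = 8% (Danish hospital J44 codes), or f = 2.1% (Swedish asthma recorded as COPD, read here as a share of COPD-coded patients).
- Missed COPD codes are set to zero, to isolate one direction. Children, who are off-label regardless of diagnosis, are ignored.

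**3. Formula.** True non-COPD share T = q + (1 - q) x f.

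- q = 10%, f = 8%: 10 + 90 x 0.08 = 17.2%
- q = 10%, f = 2.1%: 10 + 90 x 0.021 = 11.9%
- q = 5%: 12.6% (f = 8%) or 7.0% (f = 2.1%)
- q = 20%: 26.4% (f = 8%) or 21.7% (f = 2.1%)

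**4. Compare with the planned interval at q = 10%.** The last column is the f at which T passes the unrounded upper limit U, that is (U - q)/(1 - q).

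| n | Planned interval | 17.2% | 11.9% | Break-even f |
|---|---|---|---|---|
| 300 | 6.8-14.0 | outside | inside | 4.41% |
| 800 | 8.0-12.3 | outside | inside | 2.55% |
| 2,000 | 8.7-11.4 | outside | outside | 1.55% |
| 5,000 | 9.2-10.9 | outside | outside | 0.96% |

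**5. What the profile review could show.** Up to 100 profiles per drug are reviewed, 25 per age-sex cell, with no stated reweighting to the user population. The number with a COPD code is not fixed. If it were 50, then 4 false codes (8%) would give an exact 95% interval of 2.2-19.2%, and 0 false codes would still allow 7.1%. With 8 false in 100 the interval is 3.5-15.2%.

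**The case against.** The rule has a stated reason. Protocol 9.3.2.1 notes that COPD and asthma can coexist, and the label is for adults with COPD. A reader might go further than the documents allow in four ways.

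**That nothing planned reaches the on-label class.** This is not so. The profile review can sample COPD-coded adults, Shell Table 11 compares algorithm with manual classification, and the algorithm may be changed for all analyses (SAP 5.1, 7.5.2). Profiles include dispensings and procedures as well as diagnosis codes. SAP Table 4 keeps COPD with asthma as its own row, and protocol 9.7.2 reports that group. SAP 7.2 describes asthma, other respiratory history and time since first COPD diagnosis in COPD patients aged 40 or older. These checks are real but incomplete: the review's stated aim is missed codes and the time window, none separates single from repeated COPD codes, and none passes an error estimate to the prevalence.

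**That off-label use will be understated.** The documents do not support a net direction. SAP 7.3 and protocol 9.10.1 warn that hospital codes miss COPD, and in the SAP Denmark has no GP diagnoses. The true share could lie below the reported one.

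**That the quoted error rates are the study's own.** They come from hospital registers. Sweden is no longer a data source in the SAP, PHARMO has no validation figure, and France uses a recorded indication where available. Error among users of a LABA authorised only for COPD may be lower. At n = 300 or 800 the 2.1% rate leaves the result inside the interval.

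**That a two-record rule gives the other end of a range.** Repeatedly miscoded asthma would still pass it, and true COPD with one record would fail it. The improvement with two records in protocol 9.3.2.2 concerns asthma codes in Quebec and is not evidence for COPD codes.

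Finally, SAP Section 9.2 and the table shells are not among the documents supplied, so a database-specific rule there could narrow the gap.

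**Conclusion.** The point stands as a gap in the planned sensitivity analyses and does not show that the main result is wrong. One COPD code of any age decides on-label status in adults, the SAP's bias section looks in one direction only, and nothing visible quantifies the other. If the protocol's error rates carried over and 10% of users had no COPD code, false codes alone would add 1.9 to 7.2 percentage points. The larger shift lies outside the planned interval at every Table 9 size, the smaller one only from n = 2,000. Both rest on an assumed q, borrowed values of f and no missed COPD codes, so they show scale and do not estimate the bias. The R78 conflict needs none of these assumptions: the SAP gives one code two meanings, and one of them counts as COPD.

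**What to change.** Keep the current rule as the main result. In SAP 7.5.1 pre-specify, per drug and database:

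- a sensitivity result in which on-label status requires COPD records on at least two different dates;
- a separate line for adults with a single COPD record, split by asthma record yes/no, with the COPD-and-asthma row also shown in Shell Table 10.1.

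Reconcile R78 between SAP Table 5 on one side and Table 9 and the exacerbation definition in 5.3.3 on the other. Do not let R78 alone satisfy the strict rule, since two visits for acute bronchitis would otherwise meet it.

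Label the strict figure as a sensitivity result, not a bound. State that it overstates off-label use where true COPD patients have only one record, particularly in Denmark, where only hospital diagnoses are held.

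The cost is SAP wording, one extra run of the algorithm on data already held, and a few table lines.
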